8.5. Vital Signs

For each nominal time point, vital signs will be summarized in terms of observed values and changes from Baseline. Outlier values of vital signs will be flagged in the listing.

Table 5: Vital Signs Outlier Thresholds

Heart Rate (bpm)	Systolic Blood Pressure (mmHg)	Diastolic Blood Pressure (mmHg)
<40	<85	<45
>110	>160	>100

8.6. ECGs

A summary of ECG parameters, parameters reported separately QTcF, PR interval, QT interval, QRS duration, RR, and HR, will be summarized in terms of observed values and change from baseline.

Subjects without post-baseline measurement for a given treatment period will be excluded from the summary statistic (e.g., denominator of the summary statistic) for that time point.

All recorded values by central reader at ECG core lab for the standard 12-lead electrocardiogram parameters will be presented in a by-subject listing.

Outlier Analysis

The number of subjects with absolute ECG values and change from baseline in the ranges shown in [Table 6](#) will be presented in Electrocardiogram Outlier Summary by Visit and Time Point.

In addition in the same summary, QTcF will also be summarized by the following categories, Normal (males <430, females ≤450), Borderline (males (>430, ≤450); females (>450, ≤470)) and Prolonged (males >450, females >470).

Individual ECG data collected during the study will be presented in a listing. A separate listing of subjects with values of QTcF > 500 msec or an increase > 60 msec will be provided, as necessary.

Figures

Cumulative distribution plots will be provided for maximum change in QTcF at Week 12.

Investigator Assessment of ECG Readings

The investigators' assessment of ECGs as normal, abnormal and clinically significant, or abnormal but not clinically significant will be summarized for baseline and for each visit.

Table 6: ECG Outlier Thresholds

Heart Rate (bpm)	Heart Rate Change from Baseline (bpm)	PR Interval (msec)	PR Percentage Change from Baseline (%)	QRS Interval (msec)	QTcF (msec)	QTcF change from Baseline (msec)
>120	>20	> 200	> 15	> 120	Males:	≤ 30
>130	>30	> 220	> 25			≥ 430, ≤ 60
						> 60
						> 430
						> 450
						> 470
						> 480
						> 500
					Females:	
						≤ 450
						> 450
						> 470
						> 480
						> 500

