**Figure 1. Liver Chemistry Stopping Criteria and Increased Monitoring Algorithm**

## 7.2.2 QT Stopping Criteria

Study drug will be discontinued for a subject if either of the following criteria is met:

- QTcF >500 msec OR uncorrected QT >600 msec
- Change from screening or baseline in QTcF of >60 msec

One repeat ECG should be performed to confirm the accuracy and persistence of an initial result that fulfills the QT stopping criteria.

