6.5. Baseline Definition

The following table indicates the baseline to be used in the analysis.

Table 2: Baseline Specifications for Specific Variables

Parameter	Day 1 pre-dose
Laboratory (Chemistry, Hematology, Urinalysis)	x
Biomarkers	x
ECG	x
Vital signs	x
PROs	x

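### SAP 8.6 leaves a male QTcF of exactly 430 msec without a category, and its >60 msec outputs, scored from Day 1, need not reconcile with QT stops under protocol 7.2.2

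*SAP*

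**What the plan says.** **QTcF categories.** The outlier paragraph of SAP 8.6 sorts QTcF into three groups. For males, Normal is below 430, Borderline is above 430 up to and including 450, and Prolonged is above 450. For females, Normal is up to and including 450, Borderline is above 450 up to and including 470, and Prolonged is above 470.

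**Stopping rule.** Protocol 7.2.2 states: "Study drug will be discontinued for a subject if either of the following criteria is met". The first criterion is "QTcF >500 msec OR uncorrected QT >600 msec". The second is "Change from screening or baseline in QTcF of >60 msec". It adds: "One repeat ECG should be performed to confirm the accuracy and persistence of an initial result that fulfills the QT stopping criteria". The protocol's Schedule of Activities has a 12-lead ECG at screening and another on Day 1, so the two reference values are distinct.

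**Analysis reference.** SAP 6.5 introduces Table 2 with "The following table indicates the baseline to be used in the analysis". Its only column is Day 1 pre-dose, and ECG is marked there. SAP 8.6 then presents "The number of subjects with absolute ECG values and change from baseline in the ranges shown in" Table 6, whose change columns are headed as change from baseline. The sentence on the separate listing, "A separate listing of subjects with values of QTcF > 500 msec or an increase > 60 msec will be provided, as necessary", names no reference. Nor does the title of Listing 16.2.11.3 in SAP 11.3.

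**The concern.** The first matter is a plain gap. Three categories meant to classify every QTcF value omit one whole-number value for males, so a programmer must either guess or leave the record unclassified.

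The second is traceability. The SAP reuses the protocol's 500 and 60 msec thresholds, so someone reading the report will naturally take the >500/>60 listings as the set of subjects who met the QT rule. For the change criterion the SAP's reference is narrower than the protocol's. A subject could be taken off drug for a QTcF change and not appear in the >60 category. Change in ECG is among the endpoints for the primary (safety) objective, so a QT discontinuation without a matching entry in the QT outputs would prompt a query.

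**Working it through.** **1. The 430 gap.** For a male value of exactly 430: below 430 is false, above 430 is false, above 450 is false, so no category applies. For a female value of exactly 450: ≤450 is true, so Normal applies. The gap is in the SAP's prose. The corresponding male cells of Table 6 are not legible enough in the text to rely on.

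How often it would bite is a matter of assumption. Suppose male QTcF is normal, recorded to 1 msec, with 20 male ECGs. The chance per ECG is about φ((430 − mean)/SD)/SD.
- Mean 405, SD 15: φ(1.667)/15 = 0.0066, and 1 − (1 − 0.0066)^20 = 12%.
- Mean 415, SD 15: φ(1)/15 = 0.0161, and 1 − (1 − 0.0161)^20 = 28%.

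None of these inputs is in the documents, and the correction does not depend on them.

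**2. Where the references diverge.** Let S be the screening, B the Day 1 and P the post-dose QTcF. The protocol's change criterion is met if P − S > 60 or P − B > 60. The SAP's >60 category needs P − B > 60. A subject who meets the first but not the second has S + 60 < P ≤ B + 60, which requires B > S. The absolute criterion must also not apply (P ≤ 500).

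| S | B | P | P − S | P − B | Protocol change criterion | SAP >60 from Day 1 |
|---|---|---|---|---|---|---|
| 360 | 375 | 425 | +65 | +50 | met | no |
| 400 | 415 | 465 | +65 | +50 | met | no |
| 415 | 400 | 465 | +50 | +65 | met | yes |

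These values are hypothetical. In the first row the window of values missed is 420 < P ≤ 435.

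**3. Whether another SAP rule closes the difference.** The visit windows in SAP Table 3 start at Day 1, with none for screening. The fallback to a screening value in SAP 6.7.5 covers non-efficacy laboratory data with a missing baseline, not ECGs. SAP 5.1.1 does not mention the reference. No output derives change from screening or flags the protocol 7.2.2 criterion.

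**4. How often.** The documents give neither the within-subject SD nor the mean rise, so this is illustration only. Assume independent normal errors with SD 10 to 15 msec, a mean rise of 0 to 30 msec, and the three on-treatment ECGs at Weeks 4, 8 and 12.
- SD 12, rise 20: about 4.6% meet the either-reference rule and 2.5% the Day 1 rule, so 2.1% are missed. Expected number among 11: 11 × 0.021 = 0.23. Chance of at least one: 1 − (1 − 0.021)^11 = 21%.
- Same case, if one independent repeat ECG must also exceed 60: about 0.3% are missed, and 1 − (1 − 0.003)^11 = 3%.
- Whole grid: the chance of at least one miss among 11 runs from near 0% to about 74% without the repeat, and from near 0% to about 36% with it. The top end needs SD 15 and a 30 msec mean rise.

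One subject of the final 11 (SAP 4.3) is 1/11 = 9%.

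**The case against.** The strongest reply is that Day 1 is the reference both documents plan for analysis. Protocol 9.3.1 plans change from baseline, SAP 3.2.1 defines the ECG endpoint that way, and protocol 9.3.5 promises only listings, descriptive statistics and a frequency table of investigator assessments. A stopping rule is a trigger for action at the site, not an endpoint, and no count of QT-rule events is promised. Day 1 is also sensible: screening can be 12 weeks earlier, and for rollover subjects the screening ECG may come from an earlier visit still. A second noisy reference adds flags without adding drug effect. All of this stands.

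Three stronger readings are tempting, and the documents do not support them.
- *A stopped subject would vanish from the report.* Protocol 8.2.1 makes a test result that leads to discontinuation an adverse event, so it belongs in Table 14.3.3.6.1 and Listing 16.2.7.2. Discontinuations are in Listing 16.2.1.2, and every ECG value is in Listing 16.2.11.1.
- *Such a subject would show no QTcF signal at all.* At SD 12 and rise 20, about 80% of missed subjects still exceed +30 msec from Day 1, and the absolute thresholds also apply.
- *Some 40% to 50% of QT stops would be missed.* That is a share of an often rare event under assumed inputs, and it ignores the confirmatory repeat. Protocol 2.2.4 reports no clinically significant ECG alterations in Phase 1 and no meaningful ECG changes in Cohort A through 600 mg QD, so nothing supports a large mean rise.

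That the listing uses Day 1 is itself an inference from Table 2, since neither its sentence nor its title names a reference.

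The protocol's uncorrected QT >600 limit is also absent from the SAP's thresholds. It adds little: QT 600 with QTcF 500 implies RR = (600/500)^3 = 1.728 s, or 34.7 beats per minute.

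**Conclusion.** The 430 gap is wrong as written and should be corrected, however rarely it would matter.

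The difference in reference is real but is not an error in the planned analysis. Its consequence is limited: a subject stopped under the protocol's change criterion can be absent from the >60 category of Table 6 and, if it follows Table 2, from Listing 16.2.11.3, while remaining visible elsewhere. Its frequency rests wholly on assumed variability and mean rise, so no single percentage should be attached to it. Reporting the protocol criterion alongside the Day 1 change is an inexpensive improvement that lets a reader match QT stops to QT outputs.

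**What to change.** 1. In SAP 8.6, change male Normal to ≤430, and check that the male cells of Table 6 agree.
2. Keep change from Day 1 as the main QTcF summary. Add one row to the outlier table and one flag to Listing 16.2.11.3: *QTcF increase >60 msec from screening or Day 1 (protocol 7.2.2 criterion)*.
3. State the reference in the listing sentence and title, and say which ECG counts as screening, including for rollover subjects whose screening assessment was taken in Study SPR001-201.

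The cost is one inequality sign, one derived variable, one row, one flag and a few words. The screening ECG is already scheduled, so no new data are needed. The downside is a few extra flags from a second noisy reference, which separate labelling keeps apart from the main summary. The stopping rule itself is not touched, and no view is taken on which reference it should use.

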#### **8.1.4    Electrocardiogram**

A 12-lead ECG will be obtained using an ECG machine that automatically calculates the heart rate, QRS, QT, and QTc intervals, preferably using Fridericia's formula. Any ECG measurement assessed by the Investigator as a clinically significant abnormality should be recorded in the AE section of the eCRF and monitored until resolution.

Refer to [Section 7.2.2](#) for QT individual treatment stopping criteria and any additional ECGs that may be necessary.

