6.6.4. Visit Windows

All assessments will be summarized using analysis windows.

The terminology of unscheduled will be applied to assessments that are outside an analysis window regardless, of the nominal label associated with the assessments in the EDC system.

The following visit windows will be used in the summary of clinical data.

Table 3: Analysis Visit Windows

Nominal Period/Visit	Start (days)	Stop (days)
Baseline	1	1
Week 2 (Day 15)	2	21
Week 4 (Day 29)	22	35
Week 6 (Day 43)	36	49
Week 8 (Day 57)	50	63
Week 10 (Day 71)	64	77
Week 12 (Day 85)	78	91
Week 16 (Day 112)	92	120

Safety Endpoints

The following windows summarize the definition of treatment-emergent.

Table 4: Analysis Windows for Safety Endpoints

Window	Start	Stop
Adverse events	Sign of ICF	30 days post last dose
Treatment-emergent Adverse events, ECGs and Labs	Post first dose	Last dose + 30 days
Prior Medications	Prior to first dose	First dose
Concomitant Medications	Post first dose	Last dose + 24 hours
Post Medications	Post last dose + 24 hours	NA

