6.6.5. Multiple Assessments

In general, if multiple, valid, non-missing observations exist at a visit or collection time point then records will be chosen based on the following rules.

The record closest to the nominal time point in question.

If 2 records are equidistant: later record if the two visits.

If 2 records with same date/time: average (generally applies to assessments done in triplicate).

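### SAP 8.6 defines the QTcF distribution plot as a maximum at one visit, so as written it shows the Week 12 change and not each subject's worst on-treatment change

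*SAP*

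**What the plan says.** The plot is defined in one sentence of SAP 8.6: "Cumulative distribution plots will be provided for maximum change in QTcF at Week 12". No other sentence defines a maximum over the treatment period, and the figure index in SAP 11.3 lists no QTcF plot (it may be updated later).

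These rules decide which ECG is used:

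- **Recordings per visit.** Protocol 8.1.4: "A 12-lead ECG will be obtained using an ECG machine that automatically calculates the heart rate, QRS, QT, and QTc intervals". No replicates are specified.
- **Schedule.** Protocol 1.3 and SAP 4.5 both mark ECGs at screening, baseline and Weeks 4, 8 and 12. SAP 4.5 also marks one in the Follow-up/ET column; protocol 1.3 does not.
- **Visit assignment.** SAP 6.6.4: "All assessments will be summarized using analysis windows". The Week 12 window is Days 78 to 91.
- **Records per window.** SAP 6.6.5 chooses first "The record closest to the nominal time point in question", then the later of two equidistant records. It averages only records with the same date and time.
- **Missing ECGs.** SAP 8.6: "Subjects without post-baseline measurement for a given treatment period will be excluded from the summary statistic". Carrying the last observation forward (SAP 6.7.1) applies to hormones only.

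Two nearby rules also matter. The QTcF categories in SAP 8.6 begin "Normal (males <430, females ≤450), Borderline (males (>430, ≤450". The stopping rule in protocol 7.2.2 includes "Change from screening or baseline in QTcF of >60 msec". SAP 6.5 fixes the reference for analysis ("The following table indicates the baseline to be used in the analysis"), and its Table 2 gives only Day 1 pre-dose for ECGs.

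**The concern.** A maximum change is a per-subject summary over several post-dose ECGs. Tied to one visit with one retained record, the word has nothing to act on. A programmer following the sentence would plot the Week 12 change under a title that promises the worst change.

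Change in ECG is among the primary safety endpoints (protocol, Section 3). For anyone treated to Week 12, the error can only make the picture more favourable. The subjects most likely to be missing or misrepresented are those with the largest prolongation, because the stopping rule takes them off drug before Week 12. With a final sample of 11 (SAP 4.3), each subject is 1/11 = 9.1% of the distribution.

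**Working it through.** The plan gives no numerical figure for this plot, so there is none to reproduce. The check has four parts.

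**1. What a completer contributes.** Scheduled on-treatment ECGs: 3 (Weeks 4, 8, 12). Records in Days 78 to 91 after SAP 6.6.5: 1. The maximum of one value is that value. Hypothetical changes of +55, +35 and +5 msec at Weeks 4, 8 and 12 would be plotted as +5.

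**2. What a subject stopped early contributes.** The follow-up visit is 30 days after the last dose, ±7 days. Take the last dose as the evening before the ECG that triggers stopping.

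| Stop near | Last dose | Follow-up day (range) | SAP window |
|---|---|---|---|
| Week 4 | Day 28 | 28 + 30 = 58 (51 to 65) | Week 8 or Week 10 |
| Week 8 | Day 56 | 56 + 30 = 86 (79 to 93) | Week 12; Week 16 if after Day 91 |

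An on-time follow-up visit falls in the Week 12 window when 78 ≤ last dose + 30 ≤ 91, that is, for a last dose on Days 48 to 61. With the ±7 days, the range is Days 41 to 68.

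So a subject stopped near Week 4 has no Week 12 value from that visit and is absent, unless another ECG happens to be taken in Days 78 to 91. A subject stopped near Week 8 can be plotted if an ECG is done at follow-up. That value is about 30 days off drug, close to the 32 to 44 days that protocol 4.2 gives for essentially complete elimination.

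**3. Illustrative size for completers.** The documents give no SD or between-visit correlation for QTcF change, so these are assumptions. For three exchangeable normal values:

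- Probability that the maximum is not at Week 12: 2/3 = 67%. This needs only exchangeability.
- Expected maximum minus expected single value: 0.846 × SD × √(1 − ρ).

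| SD (msec) | ρ | Excess (msec) |
|---|---|---|
| 8 | 0.7 | 0.846 × 8 × 0.548 = 3.7 |
| 10 | 0.5 | 0.846 × 10 × 0.707 = 6.0 |
| 15 | 0.5 | 0.846 × 15 × 0.707 = 9.0 |
| 20 | 0.3 | 0.846 × 20 × 0.837 = 14.2 |

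At SD 15, ρ 0.5 and no drug effect, simulation puts the chance of exceeding 30 msec at about 5.7% for the maximum and 2.3% for Week 12 alone. The excess does not depend on the mean effect: with no effect the means are 9.0 and 0.0, and with a true effect of 10 msec they are 19.0 and 10.0. It is therefore a property of taking a maximum, not missed drug effect.

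**4. The neighbouring rules.**

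- Males are Normal below 430 and Borderline above 430, so exactly 430 has no category; the female rule at 450 has no such gap. If male QTcF has mean 400 to 420 and SD 15 to 20 (assumed), an integer reading of 430 occurs in about 0.4% to 2% of ECGs.
- A subject at +62 msec from screening and +50 msec from Day 1 meets the change criterion in protocol 7.2.2 but does not enter a listing of increases above 60 msec built on the Day 1 baseline.

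**The case against.** The strongest reply is that little information is lost. SAP 8.6 also provides QTcF change by visit, threshold counts by visit and time point, a by-subject listing of all ECG values, and a listing of QTcF above 500 msec or increases above 60 msec. The index carries these as Tables 14.3.7.1.6 and 14.3.7.3 and Listings 16.2.11.1 to 16.2.11.3. With 11 subjects, every value can be read directly. Table 14.3.7.2, a threshold summary whose content is not described, may also be per subject. This stands, and it limits the point to one figure. One gap remains: the by-visit tables keep one record per window, so a confirmatory repeat may be seen only in the listings.

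A second reply is that the wording is a slip for through Week 12. That is plausible: SAP Table 4 defines treatment-emergent ECGs as running from first dose to 30 days after last dose. But the SAP does not settle it, and the literal text gives a different plot.

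A reader might also infer two stronger things that the documents do not support. The first is that every subject stopped early for QT prolongation is left out. Subjects may stop drug and stay in follow-up (protocol 7.2), and the SAP schedule has a Follow-up/ET ECG, so some would be plotted with an off-drug value. The second is that the plot hides a drug effect of 6 to 14 msec. That range comes from assumed SDs of 10 to 20 and correlations of 0.3 to 0.5. It also appears in full when the true effect is zero.

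Finally, the listing of increases above 60 msec is an analysis output and need not reproduce a stopping rule. That is fair, so the screening reference is offered only as an option.

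**Conclusion.** The point holds for this plot. As written, it is the distribution of Week 12 change. It omits the Week 4 and Week 8 peaks, and it either drops subjects stopped early for QT prolongation or can show them off drug. For completers the direction is certain: the plotted value is never above the true maximum. Under exchangeable visits it is below for two of three subjects. The size in msec is illustrative only. One subject missing or misplaced is 9.1% of the distribution.

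It does not follow that early QT prolongation goes unreported, or that the trial's QT assessment as a whole is biased, since other outputs keep the values. The gap at 430 msec is a small but definite rule error. The Follow-up/ET ECG is a discrepancy between the two schedules as they read here, and it decides which subjects can acquire an off-drug value in the Week 12 window.

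**What to change.** Replace the sentence in SAP 8.6 with:

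> *Cumulative distribution plots will be provided for each subject's maximum post-baseline on-treatment change in QTcF, from first dose through Week 12 or early termination, including unscheduled and repeat ECGs (an exception to Section 6), for all Safety subjects with a baseline and at least one post-baseline ECG.*

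Then:

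- State that the exception covers both the limit to scheduled or windowed data and the one-record rule in 6.6.5.
- Define on-treatment by time since last dose, so that the Week 12 and early termination ECGs count and the 30-day follow-up ECG does not. This is narrower than the interval in SAP Table 4, so say so. Show off-drug ECGs separately.
- Add the figure to SAP 11.3, with a footnote that a maximum over several ECGs is raised by noise and that the by-visit changes describe the average effect.
- Set the male Normal category to ≤430.
- Optionally, flag in the listing of increases above 60 msec those measured from screening as well as from Day 1, to match the reference in protocol 7.2.2.
- Reconcile the Follow-up/ET ECG between protocol 1.3 and SAP 4.5.

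The cost is a few wording edits and one index entry, using ECGs already collected. The plotted distribution will move somewhat to the right.

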8.7. Hospital Anxiety and Depression Scale

Hospital Anxiety and Depression Scale is a 14-question scale. Seven questions compose the anxiety domain with scores of 0 to 3 with 3 representing a maximum response and 0 representing a minimal response. Seven questions compose the depression domain with scores of 0 to 3 with 3 representing a minimal response and 0 representing a maximal response.

The summary will summarize the anxiety, depression and total scores at each time point using a continuous reporting format.

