#### **7.2.5 Depression Stopping Criteria**

Individuals who score >12 on either the depression or anxiety subscale of the HADS (see [Section 8.1.6.2](#)) at screening or baseline are generally not eligible for this study. The Investigator should immediately contact the Medical Monitor to discuss possible study drug discontinuation and appropriate safety follow-up for a subject who scores >12 on either the depression or anxiety subscale of the HADS at any visit after baseline. This will also be considered an AESI (see [Section 8.2.8](#)). Reasons for an elevated HADS score (aside from clinical depression) include chronic pain and stress.

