### **8.1.6.2 Hospital Anxiety and Depression Scale**

Subject anxiety and depression will be monitored during the study using the HADS. The HADS ([Zigmond and Snaith, 1983](#)) is a widely used and relatively simple subject-reported instrument that focuses on subjective disturbances of mood rather than physical signs. The scale consists of 14 items, 7 items each for anxiety and depression. Each item is rated on a 4-point scale based on the frequency of symptoms over the preceding week and ranging from 0 (not at all) to 3 (very often).

Refer to [Section 7.2.5](#) for depression individual treatment stopping criteria.

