### **8.2.8 Adverse Events of Special Interest**

AESIs are those AEs that do not meet SAE criteria but must be monitored on an ongoing basis. These events will be reported on the SAE Report Form, allowing for the collection of additional information, as warranted. The following will be considered AESIs for this study:

- Suicidality as indicated by type 3, 4, or 5 ideation on the C-SSRS (see [Section 7.2.3](#) regarding study drug stopping criteria and [Section 8.1.6.1](#) regarding the C-SSRS). This should be reported as an AESI until it becomes serious according to the SAE definition (e.g. hospitalization).
- High HADS score or other indication of worsening depression (see [Section 7.2.5](#) regarding study drug discontinuation and [Section 8.1.6.2](#) regarding the HADS)
- Significant liver chemistry changes that do not satisfy stopping rules (see [Section 7.2.1](#) and [Section 12.2.1](#)). Cases of Hy's Law should be reported as SAEs.
- Severity Grade 3 or higher TEAE considered related to study drug (see [Section 7.1](#) regarding dose reduction)

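### SAP 8.7 scores the HADS depression items in the opposite direction to the protocol, so the depression summary reverses and the total no longer measures overall distress

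*SAP*

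**What the plan says.** SAP 8.7 describes the two HADS domains in consecutive sentences. For anxiety: "Seven questions compose the anxiety domain with scores of 0 to 3 with 3 representing a maximum response and 0 representing a minimal response". For depression: "Seven questions compose the depression domain with scores of 0 to 3 with 3 representing a minimal response and 0 representing a maximal response". It then specifies the output: "The summary will summarize the anxiety, depression and total scores at each time point using a continuous reporting format". It gives no formula for the total and no instruction to recode any item. The planned output is Table 14.3.8.1, by visit, on the Safety set.

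Protocol 8.1.6.2 describes the same instrument without splitting the direction by domain: "The scale consists of 14 items, 7 items each for anxiety and depression", and "Each item is rated on a 4-point scale based on the frequency of symptoms over the preceding week and ranging from 0 (not at all)", with 3 at the very-often end.

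The rest of the protocol relies on that single direction. Section 7.2.5 calls for contact with the Medical Monitor, and an AESI, for "a subject who scores >12 on either the depression or anxiety subscale of the HADS at any visit after baseline". Section 8.2.8 lists as an AESI a "High HADS score or other indication of worsening depression". Sections 5.1.2 and 5.2.3 exclude people scoring above 12 on either subscale at screening or baseline.

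Change in HADS is listed under the primary (safety) objective in Protocol section 3. SAP 3.2.1 places HADS among its additional safety endpoints. SAP 5.1.1, which records departures from the protocol's analyses, does not mention HADS scoring.

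**The concern.** The two documents give opposite meanings to the same depression score. A programmer working from SAP 8.7 would produce a depression subscale that falls as depression worsens, next to an anxiety subscale that rises as anxiety worsens. Any total built from the two would combine scores running in opposite directions.

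This matters because mood is a named safety question here. Protocol 7.2.3 regards SPR001 as CNS-active, and HADS sits under the primary objective. A reader of Table 14.3.8.1 who assumes that higher is worse, as the protocol does, would take a worsening of depression for an improvement. In the total, worsening on both subscales could appear as no change at all.

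**Working it through.** **Inputs.** Seven items per domain, each scored 0 to 3 (SAP 8.7 and Protocol 8.1.6.2). The SAP reverses the depression items only. The threshold is a score above 12 on either subscale (Protocol 7.2.5). The plan gives no HADS figure to reproduce, and no sample size or power depends on this point, so the check is score arithmetic.

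**Assumption.** The total is the plain sum of the two subscales. The SAP does not say so, but it is the natural reading of a 14-item, two-domain scale.

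**Formulas.** Let A and D be the anxiety and depression scores in the protocol's direction.

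- Subscale maximum: 7 × 3 = 21. Total maximum: 2 × 21 = 42.
- Each reversed item is 3 minus its protocol value, so the SAP depression score is 21 − D.
- Protocol total: A + D. SAP total: A + 21 − D = 21 + (A − D).
- Change in total: ΔA + ΔD under the protocol, ΔA − ΔD under the SAP.

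**Effect on the depression score.**

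| D (protocol) | Score under SAP 8.7 | Protocol above 12? | SAP above 12? |
|---|---|---|---|
| 0 | 21 | no | yes |
| 8 | 13 | no | yes |
| 9 | 12 | no | no |
| 12 | 9 | no | no |
| 13 | 8 | yes | no |
| 21 | 0 | yes | no |

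21 − D exceeds 12 whenever D is 8 or less. The two directions agree on the threshold only for D from 9 to 12. Subjects within the protocol's entry limit (D from 0 to 12) would be tabulated at 21 down to 9, and a symptom-free subject would appear at the maximum.

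**Effect on the total.** For illustration, take a subject with assumed baseline values A = 6 and D = 6. The changes do not depend on these starting values.

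| Change in A, change in D | Protocol total | SAP total |
|---|---|---|
| +5, +5 | 12 to 22 (+10) | 21 to 21 (0) |
| 0, +7 | 12 to 19 (+7) | 21 to 14 (−7) |
| +3, +7 | 12 to 22 (+10) | 21 to 17 (−4) |
| +5, 0 | 12 to 17 (+5) | 21 to 26 (+5) |
| +5, −5 | 12 to 12 (0) | 21 to 31 (+10) |

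Exact cancellation needs equal worsening on both subscales. When depression worsens more than anxiety, the total points the wrong way. When only anxiety changes, the change in the total is correct.

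**Weight of one subject.** SAP 4.3 gives a final sample of 11. If one subject's depression worsens by 7 points, the mean moves by 7/11 = 0.64: upward in the protocol's direction, downward in the SAP's.

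**The case against.** The strongest reply is that the SAP sentence may be loose wording rather than a programming instruction. It speaks of a response, not a symptom, and does not define the term. Neither document reproduces the HADS items, so it might describe how raw answers are stored or how strongly an item is endorsed as worded. The SAP writes out no formula for the total, so cancellation is inferred. The two subscales are also reported separately, and a by-subject HADS listing (16.2.6.3) would let a reader check 11 subjects directly. The above-12 rule is applied by investigators during the study, not by the SAP's tables. The analysis is descriptive, with no HADS hypothesis test, in a single-arm study.

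Much of this stands as a limit on the harm. The anxiety row is sound, full cancellation is a special case, and the documents do not show that eligibility or AESI decisions would be reversed. None of it supplies a reading under which the SAP matches the protocol. If the sentence is a slip, it needs correcting. If it describes stored raw values, the SAP lacks the recoding step needed before a subscale or total is formed.

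A count of subjects above 12 is a separate matter. Protocol 9.3.5 asks only for descriptive statistics on HADS, which SAP 8.7 provides. The same section does call for AESIs to be summarized, and the SAP's table index has no AESI table, so the count would be useful. The scoring point does not depend on it.

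**Conclusion.** The concern holds, and the sentence must be corrected before tables are programmed. As written, SAP 8.7 contradicts Protocol 8.1.6.2 and the high-score-is-worse rules in Protocol 7.2.5 and 8.2.8, and the departure is not declared.

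The reversal of the depression row follows directly from the SAP's words, provided no unstated recoding is done. The distortion of the total also assumes a plain sum. The damage is confined to the depression and total rows of Table 14.3.8.1 and to any above-12 check run on SAP-derived scores.

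**What to change.** Replace the two scoring sentences in SAP 8.7 with one definition consistent with Protocol 8.1.6.2:

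- All 14 items are scored 0 to 3, with 3 the most symptomatic. Any item stored the other way is recoded first.
- Each subscale is the sum of its seven items, range 0 to 21.
- The total is anxiety plus depression, range 0 to 42.
- Higher is worse on all three scores.

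Optionally, add a row per visit to Table 14.3.8.1 counting subjects with anxiety above 12 or depression above 12. This uses the protocol's existing threshold and sets no new clinical rule.

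The cost is a short text change and, if wanted, one table row. No new data are needed.
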